4.2 Recruitment/Screening Procedures

Research interns will review the electronic medical record for patients who are scheduled to visit each of the participating clinics. They will screen the record for the past 18 months to ensure that the eligibility criteria are met and that no exclusionary criteria exist (the REDCap screening instrument is provided in Appendix 3). If they are unsure about any of the inclusion/exclusion criteria for a specific patient, they will defer to the medical staff in the clinic.

Inclusion Criteria:

- English or Spanish speaking males and females.
- 21 – 100 years of age.
- Clinic measured blood pressure of ≥ 145 mmHg or ≥ 95 mmHg at two previous clinic visits or one previous clinic visit and on the day of enrollment. Previous clinic visit BPs must be within the past 18 months and measured at least 2 weeks apart from each other.
- Lives in a zip code that is scored as a 4-10 on the Rural-Urban Commuting Area (RUCA) Codes.

Exclusion Criteria:

- Currently pregnant or planning to become pregnant in the next year.
- Upper arm circumference greater than 50 cm (20 in)
- Prisoner status.
- Unable to provide own informed consent.

Once a potential participant has been identified, the research intern will notify the appropriate medical staff that the patient is eligible for the study. If the medical staff confirms that the BP study is appropriate for the patient, they will inform the patient about the study

during the appointment and ask for permission for the research intern to explain the study further. If the patient is interested in learning more, the research intern will either meet with the patient in the exam room, or move the patient to a research-dedicated room, whichever has a lesser impact on clinic flow for that day. The screening questions will be reviewed again with the patient to ensure accuracy (particularly whether or not a female patient is planning to become pregnant in the next year, as that will not be reflected in the medical record).

If a patient indicates that they are not interested in participating in the study at any time, they will be thanked for their time and allowed to leave the clinic.

If all eligibility criteria are confirmed and they wish to participate, the research intern will describe the study, give the patient time to read the consent form, and answer any questions that the patient may have. Specifically, the research intern will explain the following areas of the consent document:

- Purpose of the research study, duration of study participation, and the number of research visits and study contacts (i.e., texting, phone calls, emails) required.
- The study procedures and requirements.
- The risks of the study.
- The voluntary nature of the study. The participant may drop out of the study at any time.
- That their decision to participate or not will have no effect on their relationship with or care from their physician or on the clinical care that they receive.
- HIPAA information: The research team must have access to the participant's medical information and to create medical information in order for the participant to be in the study; the investigators will obtain medical record data for the time period that spans 18 months preceding enrollment until 12 months following enrollment.
- The research-related injury section.
- Contact information that participants can use to reach investigators for study-related issues.

If the patient agrees to participate, they will be asked to sign two copies of the consent form. The research intern will sign the consent forms as the witness. One copy will be given to the participant and one copy will be kept and filed securely in the research team office. The patient will be enrolled in the research study in the electronic medical record via IRB and hospital policy.

Patients may take an unsigned consent form with them to think about participation. They will be given contact information to schedule a follow-up appointment with an intern at a later date if they choose to participate.

Patients may also sign the consent form but schedule completion of other baseline activities for a later date to meet their scheduling needs.

The English and Spanish consent forms are provided in Appendix 4.

4.3 Baseline Visit Procedures

4.3.1 Baseline Data Collection

After the consent form has been signed, the research intern will continue with the other baseline activities. Together, the intern and participant will complete the demographic information that is collected on the Baseline Data REDCap form (Appendix 5).

4.3.2 Blood Pressure Measurement

Trained research interns will measure the participant's blood pressure and document it on the Baseline Data REDCap form (Appendix 5). All measurements will be taken using the Omron HEM-907-XL using the following procedures:

Prepare the Participant:

- Participants should refrain from smoking for 20 minutes prior to the blood pressure measurement.
- The participant should remove all clothing that covers the location of the cuff placement.
- The participant should be comfortably seated in a chair, with the back supported, legs uncrossed and flat on the floor, the arm supported at heart level on a desk, with the palm facing upward.
- The participant should sit for at least 5 minutes before the first measurement and should relax as much as possible.

Cuff Measurement:

- The participant's arm circumference should be measured during screening to ensure the appropriate size cuff is used and to exclude morbidly obese participants where the cuff size is too small for their arm. The appropriate cuff should be chosen based on the measurement ranges specified for each cuff. If an arm measurement falls on a number that is specified for two cuffs, both cuffs should be placed on the arm sequentially and the cuff for which the **INDEX ↑** arrow that is marked on the cuff falls within the range bar should be chosen.
- If upper arm circumference is >50 cm (20 in) the participant will be thanked and excluded from the study.

Cuff Placement:

- Do not allow a sleeve to form a tourniquet on the arm.
- Palpate the brachial artery in the antecubital fossa and place the **ART ↓** that is marked on the midline of the bladder of the cuff so that it is over the arterial pulsation of the participant's bare upper arm.

- The lower end of the cuff should be ½ to 1 inch above the inner side of the elbow joint.
- The middle of the cuff should be at the level of the right atrium (the mid-point of the sternum).
- Place the cuff snugly around the bare upper arm so that you can only insert one finger between the cuff and the arm.

Blood Pressure Measurement:

- Use the Omron HEB-907-XL and record values in the Baseline Data REDCap form (Appendix 5).
- Tell the participant that you will be taking 3-4 blood pressure measurements and that neither of you should talk during the measurements.
 - Take a single sitting BP reading with the MODE set to “SINGLE” and record. Wait at least 60 seconds before taking the next blood pressure.
 - Repeat this two more times.
 - The average of the 2nd and 3rd readings will be used as the research BP for this visit.
 - If the 2nd and 3rd BP values are more than 4 mmHg apart, a 4th value will be obtained and the two nearest values will be averaged. This will serve as the research BP for that visit.

IF YOU GET AN ERROR MESSAGE AT ANY POINT, START THE SEQUENCE OVER.

4.3.3 Blood Pressure Medications

Research interns will record all BP medications (and dosage) that the participants are currently taking at the baseline appointment in the REDCap BP Medication Form (Appendix 6). This REDCap form is linked to the Master Drug Data Base Clinical Drugs BioPortal Ontology Service so that when a research intern begins typing a medication name, an appropriate spelling of the drug and all of the available dosages will automatically populate. This will substantially reduce data entry mistakes. If a participant is taking more than one BP medication, the REDcap form will allow them to create multiple entries. The research interns will use the updated Drug Codes for Antihypertensive Agents form used in the CAPTION trial to help them determine which of the patient’s medications are appropriate to record (Appendix 7).

4.3.4 Enrollment in WyBP

Before leaving the baseline appointment, the participants will need to be enrolled in WyBP so that they can send home-BP measurements via text message.

- Go to <https://vinci.cs.uiowa.edu/meditext2/home/>
- Log in with your username and password.
- Select the PharmText BP study from the dropdown menu.
- Click the green Enroll Patient button in the top right corner.
- Enter the participant’s phone number starting with the area code, click Next.

- Enter the participant's Record ID from REDCap in the Subject identifier field.
- Leave the email field blank.
- Choose the participant's preferred language (English or Spanish), click Submit.
- You will be taken to an Edit Patient screen that shows the phone number you just registered along with a note at the top saying that the patient was successfully created in the study. Click the green Update button to be taken to the next step.
- Back at the Home Screen, you will see that the Study Summary now shows an additional enrollment and progress made toward the overall enrollment goal. Click the Patients button to assign text message subscriptions to the participant you just enrolled.
- Click on the Patient for whom you need to assign a text message subscription.
- Click the green Add Subscription button in the top right corner.
- Choose the PharmText Baseline Protocol. Set the Start Date to be tomorrow's date. Set the End Date to be 15 days from tomorrow. Set the frequency to 1. Choose the appropriate morning and evening Send Times for the participant to receive the text messages (NOTE: the morning Send Time should be a time after the patient will wake up, but before they take any morning medications. The evening Send Time should be a time that is convenient for the participant between dinner and going to bed.). Make sure both the Send End Message and Send End Email to Managers are checked. Click the green Submit button.

A second set of subscriptions will need to be created for all intervention participants so that they can send their 3 days of BPs each month. These subscriptions will be created by our software developer (unblinded). He will check REDCap once per week to see which new participants have been randomized to the intervention group. Then, he will create subscriptions for them to send 3 days of BPs each month beginning on the date that the participant was enrolled (i.e., if a participant was enrolled on August 15, they will submit their first day of BPs on the 15th, 16th, and 17th of each month throughout follow up). This strategy will allow the pharmacists to see a variety of BPs from different days of the week. The software developer will create the subscriptions using these steps:

- Create subscriptions 2-12 for the participant for the 3 days of text messages each month throughout the 12 months of follow up.
- Click the Patients button to assign a subscription to the appropriate participant.
- Click on the Patient for whom you need to assign a text message subscription.
- Click the green Add Subscription button in the top right corner.
- Choose the PharmText Ongoing Protocol. Set the Start Date to be today's date next month (i.e., if the participant enrolled on April 15th, you would set this Start Date to be May 15th). Set the End Date to be 2 days later. Set the frequency to 1. Choose the same morning and evening Send Times as the previous subscription. Do not check the Send End Message and Send End Email to Managers options until you are creating the final subscription.

4.3.5 Compensation

Once a participant has completed the baseline appointment, a research intern will submit a form for a \$50 compensation check to be mailed to the participant's home using the university's online eVoucher system. They will log this submission using the REDCap Compensation Form (Appendix 8).

4.4 Randomization and Treatment Arms

[name] created the stratified randomization lists for each clinic site. These lists are being uploaded to a website created by our software developer (unblinded). As participants have completed their home BP measurements, the research pharmacists will log into this website using a unique username and password. They will input the Record ID for the participant they need to randomize as well as the clinic location from which the participant enrolled. The website will inform the pharmacist of group assignment and they will record that in the Group Assignment REDCap form (Appendix 9). The website will store a log with a date and time stamp of which pharmacist randomized each participant to ensure that pharmacists do not intentionally or unintentionally alter the randomization in any way. This strategy should ensure that a relatively equal number of intervention and control participants are enrolled at each clinic.

4.4.1 Control Group:

Once the research pharmacist is informed of the participant's group assignment, they will contact the participants. The pharmacist will discuss their home BP measurements and only provide general education on hypertension. If the BP values remain elevated on home monitoring, the pharmacist will advise the participant to make an appointment with their physician to address BP elevations. This will be the only pharmacist contact for the control group.

4.4.2 Intervention Group:

The pharmacists will have access to the participants' electronic medical records, all information collected by the research interns, and the home BP values that are submitted via text message. Pharmacists will employ a patient-centered approach to improve participant's BP by providing support, education, and recommendations for treatment intensification, as necessary. They will communicate with participants via phone, text message, or email, based on participant preferences. They will not follow a specific protocol, but will base treatment decisions on current BP guidelines. They may schedule more home BP measurements than the 3 days per month. Recommendations to physicians will primarily be made through the electronic medical record to quickly improve BP control. They will also recommend laboratory testing if indicated (e.g., serum potassium or creatinine).

The pharmacists will review the home BP values with the intervention subjects. If the home BP values are controlled, the pharmacist will continue to monitor home BP values.

However, if the pharmacist identifies issues such as poor medication adherence, inability to afford medications or other issues, they will work with the patient and physician to optimize therapy and/or reduce cost. If the pharmacist suspects white coat hypertension, they will make a recommendation to the physician to refer the patient to the University of Iowa ambulatory blood pressure service.

If BP values are elevated, the pharmacist will assess medication adherence, ability to pay for medications and whether the regimen is optimal to control BP based on patient demographics and co-existing conditions. The pharmacist will communicate recommendations for lifestyle and other changes directly to the subject. If medication changes are needed, the pharmacist will communicate to the physician through the electronic medical record. The pharmacist may recommend:

1. Increased dose of a medication.
2. Addition of a medication.
3. Discontinuation of a medication.
4. Modification of the regimen to optimize therapy, improve convenience (e.g. fixed-dose combinations) or reduce cost.

All participants in the pharmacist intervention group will continue to have access to a research pharmacist for the entire 12 months of follow up. Additionally, they will be asked to continue measuring and texting BP values (1 morning, 1 evening) for 3 days each month throughout the 12-month follow up.

The pharmacists will typically contact with the participants every 2 weeks while BP is not controlled. Once BP is controlled, they will continue monitoring the participant's records and home BPs and make contact at least every 2 months to support adherence and reassess BP control.

The REDCap forms that the pharmacists will use to record data are shown in Appendix 10

4.5 6-Month Visit Procedures

All participants will be asked to return to the clinic where they enrolled at for a 6-Month appointment with a research intern. To allow for flexibility with scheduling, 6-Month appointments will be allowed to occur anytime between 5 Months and 7 Months after the enrollment date. This BP value will be the outcome BP value. If a participant is not able to make it to the clinic during this window, but does want to come in after the 7 Month date, this will be allowed and all data will be collected, however, it will not be counted in the 6-month outcome and the 6-month outcome will be considered missing. In this case, a note will be placed in the participant's record and these data may not be used in analyses.

At the 6-Month appointment, the research intern will collect the research BP values, any BP medications that the participants are currently taking, the last 3 BP values that were

recorded by the participant's home BP cuff, and test the home BP cuff for accuracy. If the home BP cuff appears to be measuring inaccurately, it will be replaced. The participant will be sent another \$50 compensation check. All of the procedures outlined at baseline will be followed again, but the data will be collected on separate 6 Month REDCap forms (not shown).

4.6 12-Month Visit Procedures

All participants will be asked to return to the clinic for a 12-Month appointment with a research intern. To allow for flexibility with scheduling, 12 Month appointments will be allowed to occur anytime between 11 Months and 13 Months after the enrollment date. If a participant is not able to make it to the clinic during this window, these data will be missing.

At the 12-Month appointment, the research intern will collect the research BP values, any BP medications that the participants are currently taking, a 12-Month Exit Survey (Appendix 11) asking for the participant's feedback about the study, and send another \$50 compensation check. All of the procedures outlined at baseline will be followed again, but the data will be collected on separate 12-Month REDCap forms (not shown). Participants will also be asked about any hospitalizations or emergency room visits that occurred over the 12-month follow up period, especially those that occurred outside of the University of Iowa system (Appendix 12).

Additionally, the research team will conduct a 12-Month Medical Record Review for each participant. This chart review will occur separately from the 12-Month visit and will not require any effort on the part of the participant. A member of the research team will screen the participant's medical record for all clinic/quick care visits (documenting reason), any emergency room visits (documenting reason), and any hospitalizations (documenting reason and length of stay). These data will be recorded on the REDCap forms in Appendix 13. Again, multiple entries will be allowed by REDCap.

4.7 Adverse Event Reporting and Determination

As this is a low-risk study, we do not anticipate many adverse events. However, if any member of the research team becomes aware of a potential adverse event, they will report it to [name] ([contact]). He will review the event and make a ruling as to whether the adverse event is related to the study or not. If he determines that an adverse event has occurred, the DSMB and IRB will be notified as quickly as possible. Until an official ruling has been made by [name], other members of the research team should not be notified, because they are blinded to group assignment.

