Appendix 10: Pharmacist REDCap Forms

Scheduling Call

Record ID

Date of Scheduling Call

Time of Scheduling Call

Encounter Outcome

- Complete - spoke with patient
- Complete - spoke with proxy
- Complete - revised appointment date/time
- Incomplete - no answer, left message
- Incomplete - busy signal/no voicemail
- Incomplete - wrong number

Note

Follow Up

Date

Time

Form Author

Patient Follow Up

Record ID

Encounter Date

Contact Type

Patient Other (explain in comments below)

Contact Type Comments:

Encounter Length

(minutes)

Encounter Notes

Barriers/Side Effects

Barriers to Regimen/Side Effects

Adherence

of missed doses in the past week

Use of adherence tools

Medication cost concerns

Assessment/Plan

BP Goal

Patient is/is not at goal.

is
 is not

Lifestyle Changes Recommended to Patient

Lifestyle changes recommended to patient: (check all that apply)

- decrease weight
- DASH plan
- Other diet recommended
- reduce sodium
- increase activity
- decrease smoking
- increase med compliance
- other
- no lifestyle changes recommended

If other, specify here: _____

New Plan/Recommendations

New plan/recommendations

Continue current regimen
 Recommend change to plan

If recommending change to plan, list complete plan here: _____

Include:

- 1) Prescribed medication
- 2) Medication code
- 3) Change Type (a = drug started, b = dose increased, c = dose decreased, d = drug discontinued)
- 4) Dose 1
- 5) Dose 2
- 6) Unit
- 7) Frequency
- 8) Comments

Follow Up Information (if applicable)

Date

Follow Up Time_____
Follow up purpose:

Form Author

Physician Communication

Record ID

Encounter Date

Encounter Mode

EMR Email Fax Other (explain in comments below)

Encounter Comments

Provider Name

Physician Acceptance

Recommended plan accepted Recommended plan modified (list complete final plan below)
 Plan not accepted, continue previous plan

Final Plan (complete only if changed from pharmacist recommended plan)

Include:

- 1) Prescribed medication
- 2) Medication code
- 3) Change Type (a = drug started, b = dose increased, c = dose decreased, d = drug discontinued)
- 4) Dose 1
- 5) Dose 2
- 6) Unit
- 7) Frequency
- 8) Comments

Recommendation Outcome Date

Follow Up Information (if applicable)

Date

Time

Form Author

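### The only side-effect prompt in the forms shown belongs to a pharmacist form introduced for the intervention arm, so an excess of non-serious adverse events there could not be told apart from more frequent contact

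*Combined protocol and SAP*

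**What the plan says.** **How events come to light.** Section 4.7 opens with "As this is a low-risk study, we do not anticipate many adverse events". The rule is then "if any member of the research team becomes aware of a potential adverse event, they will report it". It gives no scheduled question, checklist or look-back period.

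**Where side effects are prompted.** In the forms shown, one field does this: "Barriers to Regimen/Side Effects", on the Patient Follow Up form in Appendix 10. The pharmacist forms are introduced at the end of Section 4.4.2, Intervention Group: "The REDCap forms that the pharmacists will use to record data are shown in Appendix 10".

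**Contact by arm.**
- Intervention (Section 4.4.2): "The pharmacists will typically contact with the participants every 2 weeks while BP is not controlled". Once BP is controlled, contact is at least every 2 months. Pharmacists also keep monitoring these participants' records and may recommend laboratory tests.
- Control (Section 4.4.1): "The pharmacist will discuss their home BP measurements and only provide general education on hypertension", and "This will be the only pharmacist contact for the control group".
- Both arms (Sections 4.5 and 4.6): intern visits at 6 and 12 months. The items listed are research BP, BP medications, cuff checks at 6 months, and an exit survey at 12 months. No side-effect question is listed, and the exit survey in Appendix 11 has none. The REDCap forms for these two visits are not shown.

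**What is collected alike in both arms.** At 12 months (Section 4.6), "Participants will also be asked about any hospitalizations or emergency room visits that occurred over the 12-month follow up period". Every participant also has a 12-month chart review of clinic, emergency and hospital visits with the reason for each (Section 4.6, Appendix 13).

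**The concern.** The intervention works by changing drug treatment. The Aim 2 power paragraph in Section 6 expects 4.9 medication changes per intervention participant against 1.1 per control. Tolerability of that extra treatment is the natural safety question, and non-serious side effects are where it would first show.

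As written, one arm is prompted repeatedly and the other depends on volunteering a complaint. Record monitoring and laboratory recommendations in the intervention arm push the same way. A count of reported events by arm would mix harm with opportunity to report. If the monitoring board saw more events under the intervention, it could not tell whether drug changes or phone calls produced them, and that is the result it would most need to interpret.

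**Working it through.** The documents give no adverse-event rate, detection rate or safety sample size, so there is no figure of the plan's own to reproduce on this point. The check counts contacts and then illustrates the effect of unequal detection under stated assumptions.

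**1. Contacts per participant.** Appendix 2 puts randomization and first pharmacist contact by day 18, leaving 365 − 18 = 347 days.
- Intervention, BP never controlled, every 14 days: 347 / 14 = 24.8, about 25.
- Intervention, BP controlled throughout, every 2 months (61 days): 347 / 61 = 5.7, about 6.
- Control: 1.
- Adding the two intern visits, at which either arm could volunteer a complaint: about 8 to 27 against 3.

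Whether the first call is counted within the intervention total or on top of it changes that total by one.

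**2. Recorded risk ratio when true risk is equal.** Let t be the true risk of a side effect in both arms, and dI and dC the probabilities that it is recorded. The recorded ratio is (t × dI) / (t × dC) = dI / dC, whatever t is. Assumed values:
- 0.90 / 0.60 = 1.5
- 0.90 / 0.45 = 2.0
- 0.90 / 0.30 = 3.0

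**3. Expected counts.** With 180 per arm (the completer target in Section 6) and an assumed t of 10%:
- intervention: 180 × 0.10 × 0.90 = 16.2
- control: 180 × 0.10 × 0.60 = 10.8, or 8.1 at 45% detection, or 5.4 at 30%

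**4. Chance of a falsely significant excess.** With p1 = t × dI, p2 = t × dC, p̄ their mean, n = 180 and a two-sided 5% test:

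Φ{ [(p1 − p2) − 1.96 √(2p̄(1 − p̄)/n)] / √([p1(1 − p1) + p2(1 − p2)]/n) }

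Example: p1 = 0.09 and p2 = 0.06 give (0.03 − 1.96 × 0.0278) / 0.0277 = −0.88, and Φ(−0.88) = 0.19.

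| Assumed true risk, both arms | 90% v 60% | 90% v 45% | 90% v 30% |
|---|---|---|---|
| 5% | 11% | 22% | 39% |
| 10% | 19% | 40% | 67% |
| 20% | 36% | 71% | 94% |
| 30% | 53% | 89% | over 99% |

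With equal detection the chance would be 2.5% in that direction, and the expected ratio would be 1.0 (16.2 against 16.2 events at 10% risk and 90% detection).

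**5. What the evenly collected data can show.** For emergency or hospital events captured the same way in both arms, the same formula with 180 per arm gives about 76% power for a doubling from an assumed 10% to 20%, and about 44% for a doubling from 5% to 10%. These data carry some safety information.

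**The case against.** The other side has a good case against any wider reading.

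- **A reader might infer that the trial cannot show whether intensification is safe.** The documents do not support that. Emergency, hospital and clinic-visit data are gathered identically in both arms with reasons. Their limits are that they arrive only at 12 months and that nothing stated feeds them into adverse-event reporting or a safety comparison.
- **A reader might infer that controls are never asked about side effects.** This cannot be confirmed. The 6- and 12-month forms are not shown, and the text does not say whether the Patient Follow Up form is also used for the single control call. What can be said is that none of the listed items asks.
- **A reader might infer that the plan will report a biased comparison.** Sections 5 and 6 plan no adverse-event analysis by arm. Section 4.7 describes case-by-case review, and Section 7 refers to a monitoring board charter that is not among the documents. The bias would enter only if a tally by arm were made.
- **A reader might infer that finding no excess would be uninformative.** Since the bias tends to raise the intervention count, no excess despite fuller detection would be partly reassuring.
- **The form field is general.** It covers barriers and side effects together and is not tied to dose changes.
- **Light monitoring may be proportionate** in a study that describes itself as low-risk, and no primary or secondary outcome is affected.

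All of this stands as a limit on scope. It does not remove the unequal prompting of non-serious events, and the missing arm-comparable safety summary is part of the same gap.

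**Conclusion.** The point holds for non-serious events that are recorded because someone on the team happens to learn of them. A by-arm count of these would tend to be inflated in the intervention arm, and an observed excess could not be attributed to treatment. The direction rests on one plausible assumption: more contacts and a prompt lead to more recorded events. The size is unknown. The ratios of 1.5 to 3.0, and the false-excess probabilities, follow from assumed detection and risk values and are not estimates for this trial.

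Serious harm is better covered by the data collected alike in both arms, though late and without a stated use. The efficacy analyses are untouched. This is an improvement worth making because it is cheap and the intervention is meant to produce several more drug changes per person.

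**What to change.** 1. At both the 6- and the 12-month visit, once the research BP readings are complete, have the interns ask every participant the same short, fixed list of side effects, with the same look-back period in both arms, and the Appendix 12 emergency/hospital questions.
2. State in Section 4.7 that any between-arm safety comparison uses only these visit data and the chart review. List events elicited by pharmacists separately, for the intervention arm.
3. If the forms not shown already contain such questions, say so in Sections 4.5 and 4.6 and reproduce them in an appendix.

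**Cost.** One short REDCap form at two existing visits and a sentence or two in Section 4.7, with no extra staff or visits. It adds a few minutes per visit and more minor events to review. There is a small risk that answers reveal the arm to the interns who measure the primary outcome. Asking after the BP readings protects that visit's measurement, but a 6-month answer could still be remembered at 12 months, so a different intern could take the later reading where staffing allows.

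### Section 4.7 withholds potential adverse events from the team on a blinding ground that is untrue for the pharmacists, and leaves unclear whether events ruled unrelated reach the DSMB

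*Combined protocol and SAP*

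**What the plan says.** Section 4.7 sets a single route. It states that "if any member of the research team becomes aware of a potential adverse event, they will report it to" one named person (the name is removed in the copy reviewed). Of that person it says: "He will review the event and make a ruling as to whether the adverse event is related to the study or not". Onward reporting follows from his decision: "If he determines that an adverse event has occurred, the DSMB and IRB will be notified as quickly as possible". Within the team there is silence "Until an official ruling has been made by" him; during that time, "other members of the research team should not be notified, because they are blinded to group assignment". No deadline for the ruling is given, and no team member is exempted.

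Section 4.4 describes who knows the assignment. The research pharmacists log in to randomise each participant: "The website will inform the pharmacist of group assignment", and they record it. They then contact participants in both arms. In the intervention arm they go on to advise on therapy: "If medication changes are needed, the pharmacist will communicate to the physician through the electronic medical record". Sections 4.3.4 and 4.4 both label the software developer as unblinded.

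The Protocol Synopsis calls the trial single-blind but does not say who is blinded.

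**The concern.** Two parts of Section 4.7 do not fit the rest of the protocol.

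First, the only reason given for silence is blinding, yet the silence extends to people who are not blinded. Among them are the pharmacists, who are the team members recommending changes to antihypertensive therapy. If the rule is followed, a suspected harm known to one member of the team is not passed directly to them while the ruling is pending, for as long as that takes.

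Second, one person's ruling controls what goes to the DSMB and IRB, and the text does not keep two questions apart: whether an adverse event took place, and whether the study caused it. If relatedness decides what is sent on, the DSMB sees a filtered set of events, and the filter may not act equally in the two arms. The trial is designed to produce more medication changes in one arm, so harm data that can be compared by arm are what the DSMB needs.

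**Working it through.** The point rests on no figure, so no calculation applies. The check is to set the sections side by side.

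1. **Whom the silence covers.** Section 4.7 refers to the rest of the research team without exception. The key personnel table in Section 4.1 lists the research pharmacists alongside the research interns, so on its face the rule includes the pharmacists.

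2. **Whether the reason is true of them.** Section 4.4 has the pharmacists perform the randomisation and learn the result for both arms. The reason is therefore false for the pharmacists and for the software developer. It remains coherent for the interns, who measure the outcome BP, and for any other member who is in fact blinded.

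3. **What the silence withholds in practice.** Section 4.4.2 gives the pharmacists the electronic medical record and the data that the interns collect. The follow-up form in Appendix 10 has a field for side effects. They may therefore learn of an event by reading or by asking. These channels do not fully replace notification. Section 4.7 describes a report to one person, and the list of appendices contains no adverse event form. Section 4.5 lists no question about events among the 6-month data items, although the 6-month forms are not shown. Section 4.6 places the question about hospital and emergency visits, with its emphasis on care outside the university system, at the 12-month visit, when the pharmacist service is ending.

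4. **What is ruled on and what triggers reporting.** The ruling is defined as one on relatedness to the study. The next sentence triggers notification when the person finds that there was an adverse event. There are two readings:
   - The two sentences describe one decision, so an event judged unrelated is not sent on.
   - They describe two decisions, so an unrelated adverse event is still sent on.

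   The text does not settle which is meant.

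5. **Whether another route to the DSMB exists.** Section 4.8 covers only unanticipated problems that do not involve an adverse event. The chart review in Section 4.6 collects clinic and emergency visits and hospital stays, but no link to the DSMB is stated. Section 5 lists no harm among the outcomes, and Section 6 plans no comparison of adverse events between arms. Section 7 refers to a DSMB Charter, which is not among the documents.

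6. **Whether relatedness could be judged differently by arm.** Section 4.4.1 limits controls to one pharmacist contact. Section 4.4.2 gives the intervention arm pharmacist follow-up and treatment recommendations for 12 months. The Aim 2 power paragraph in Section 6 expects 4.9 medication changes per intervention participant and 1.1 per control, a ratio of 4.9 / 1.1 = 4.5. The intervention arm thus offers more study activity to which an event could be attributed. It is plausible, though not shown, that the same event would be called related more readily there.

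**The case against.** The strongest reply is that these are faults of wording. The clause about blinding can be read as covering only those members who are blinded, since other sections openly describe the developer as unblinded and have the pharmacists learn assignments. On that reading the pharmacists were never meant to be excluded. This is a fair guess at the intention, but the sentence makes no such distinction, and staff following it literally would not tell the pharmacists.

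A second reply is that the pharmacists have wide access to data and a side-effects field on their own form, and that participants can tell them about an event directly. This stands. A reader might infer that the pharmacists would go on recommending intensification with no means of knowing of a suspected harm; the documents do not support that.

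A third reply concerns the DSMB. A reader might infer that events ruled unrelated are lost, or that the DSMB is left with no valid comparison between arms. Neither is shown. The trigger sentence does not itself mention relatedness, the Charter may provide a route, and hospital and emergency visits are collected in both arms. What stands is that the supplied documents neither guarantee that unrelated events reach the DSMB nor describe another way for them to do so.

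Two further inferences should be resisted. The wording may suggest that the person who rules is unblinded, but the documents do not say. Nor do they show that only the interns need protection: who is blinded is undefined, and others, such as the coordinator or the chart reviewers, may be.

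**Conclusion.** The point holds as an internal contradiction and an ambiguity in safety reporting. The stated ground for withholding is false for the pharmacists and the developer, and the ruling has no time limit. The effect is to deny the pharmacists direct notification; it does not leave them without information. Separately, the text leaves open whether events judged unrelated reach the DSMB, and a relatedness judgement may differ between arms.

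No numerical size can be given. The documents state no adverse event rate, no proportion expected to be judged related and no turnaround time for the ruling; Section 4.7 says only that few events are anticipated. The conclusion on the DSMB assumes that the Charter adds nothing to Section 4.7, which cannot be checked here. The conclusion on the pharmacists needs only Sections 4.4 and 4.7. The change is worth making, because it improves safety oversight for little effort.

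**What to change.** Reconcile Section 4.7 with Section 4.4 in three respects:

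- State which roles are blinded. Confine the no-notification rule to members who are actually blinded, including those who measure outcome BP, and say that it does not cover the unblinded pharmacists.
- Report all adverse events to the DSMB by arm, with the relatedness ruling attached as a label and not used as a filter. Keep the prompt notification that Section 4.7 already promises.
- Align the text with the DSMB Charter, which may already contain such a route. If it does, a cross-reference is enough.

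Nothing is proposed here on clinical management or on when a treating physician is told. The cost is a few sentences in Section 4.7, a longer DSMB listing and slightly more reporting work. Blinded members would remain under the existing restriction.
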